9.4. Analysis Populations

Analysis populations for statistical analyses are Randomization Set, Full Analysis Set (FAS), modified Intent-to-Treat (mITT) Set, PP Set, Immunogenicity Subset, Solicited Safety Set, and Safety Set, as shown in [Table 8](#).

Table 8: Populations for Analyses

Population	Description
Randomization Set	All participants who are randomized, regardless of the participants' treatment status in the study.
Full Analysis Set (FAS)	All randomized participants who received at least one dose of IP. Participants will be analyzed according to the group to which they were randomized.
Modified Intent-to-Treat (mITT) Set	All participants in the FAS who had no immunologic or virologic evidence of prior COVID-19 (ie, negative NP swab test at Day 1, and/or bAb against SARS-CoV-2 nucleocapsid below LOD or LLOQ) at Day 1 before the first dose of IP. Participants will be analyzed according to the group to which they were randomized.
Per-protocol (PP) Set	All participants in the mITT Set who received planned doses of IP per schedule and have no major protocol deviations, as determined and documented by Sponsor prior to database lock and unblinding, that impact critical or key study data. Participants will be analyzed according to the group to which they were randomized.
Immunogenicity Subset	All participants in the FAS who were sampled into a subset for characterizing mRNA-1273 immunogenicity and had a valid immunogenicity test result prior to the first dose of IP and at least 1 valid result after the first dose of IP. Participants in the subset who had major protocol deviations that impact critical or key immunogenicity or study data may be excluded from the Immunogenicity Subset. The details of the Immunogenicity Subset will be documented prior to analysis of immunogenicity data.
Solicited Safety Set	The Solicited Safety Set consists of all randomized participants who received at least one dose of IP and contributed any solicited AR data. The Solicited Safety Set will be used for the analyses of solicited ARs and participants will be included in the treatment group corresponding to the IP that they actually received.
Safety Set	All randomized participants who received at least one dose of IP. The Safety Set will be used for all analyses of safety except for the solicited ARs. Participants will be included in the treatment group corresponding to the IP that they actually received.

Abbreviations: AR = adverse reaction; bAb = binding antibody; COVID-19 = coronavirus disease 2019; IP = investigational product; LLOQ = lower limit of quantification; LOD = limit of detection; NP = nasopharyngeal; SARS-CoV-2 = severe acute respiratory syndrome coronavirus 2.

9.5. Statistical Analyses

This section provides a summary of the planned statistical analyses of the primary and secondary endpoints.

The overall Type I error rate for the primary endpoint at the IAs and the primary analysis is strictly controlled at 2.5% (1-sided) based on the Lan-DeMets O'Brien-Fleming approximation spending function (see [Section 9.6](#) for details). The primary efficacy results that will be considered statistically significant after consideration of the strategy for controlling the Type I error as described in [Section 9.6](#). Statistical significance of the primary efficacy endpoint can be achieved at either one of the IAs or at the primary analysis. A sequential/hierarchical testing procedure will be used to control Type 1 error rate over the primary efficacy endpoint and the secondary efficacy endpoints. Secondary efficacy endpoints will only be tested when the primary efficacy endpoint achieves statistical significance. Multiplicity adjustments among the secondary efficacy endpoints may be performed for secondary efficacy endpoints, in that case, will be specified in the SAP.

No formal multiple comparison adjustments will be employed for multiple safety endpoints or multiple efficacy endpoints. Nominal p-values and CIs may be computed for other efficacy analyses without controlling for multiplicity as a measure of VE.

9.5.1. Efficacy Analyses

Efficacy analyses will be performed using the FAS, mITT, and PP populations, and participants will be included in the treatment group to which they were randomized. The primary analysis population will be the PP Set.

[Table 9](#) summarizes the analysis approach for primary and secondary efficacy endpoints for Part A, the randomized, observer-blind, and placebo-controlled phase of the study. Sensitivity analysis methods are described for each endpoint as applicable.

Table 9: Statistical Analysis Methods of Efficacy Endpoints

Endpoint	Statistical Analysis Methods

Primary endpoint: Vaccine Efficacy (VE) of mRNA-1273 to prevent COVID-19
	
 • Primary analysis: VE will be estimated with $1 - HR$ (mRNA-1273 vs. placebo) using a Cox proportional hazard regression model with treatment group as a fixed effect and adjusting for stratification factor based on the PP Set, with cases counted starting 14 days after the second dose of IP. • Analysis using the same model based on the mITT Set. • Sensitivity analysis using the same model based on the PP Set, with cases counted starting either immediately after the second dose of IP or immediately after the first dose of IP.

Endpoint	Statistical Analysis Methods
	
 • Subgroup analysis of the primary efficacy endpoint will be performed to assess consistency of VE, such as in the age groups ≥ 18 and < 65 years and ≥ 65 years. • Supportive analysis of VE to be estimated with $1 - \text{ratio of incidence rates}$ with 95% CI using the exact method conditional upon the total number of cases. • Supportive analysis of cumulative incidence VE.

Secondary endpoints:
 
 • Vaccine efficacy of mRNA-1273 to prevent severe COVID-19 • Vaccine efficacy of mRNA-1273 to prevent serologically confirmed SARS-CoV-2 infection or COVID-19 regardless of symptomatology or severity • Vaccine efficacy of mRNA-1273 to prevent COVID-19 using a secondary definition of symptoms • Vaccine efficacy of mRNA-1273 to prevent death due to COVID-19 • Vaccine efficacy of mRNA-1273 to prevent COVID-19 after the first dose of IP • Vaccine efficacy of mRNA-1273 to prevent asymptomatic SARS-CoV-2 infection 	
Similar analysis method as for the primary endpoint analysis. For each of the secondary endpoints:
 
 • Primary analysis: VE will be estimated with $1 - \text{HR}$ (mRNA-1273 vs. placebo) using a Cox proportional hazard regression model with treatment group as a fixed effect and adjusting for stratification factor based on the PP Set, with cases counted starting 14 days after the second dose of IP. • Analysis using the same model based on the mITT Set. • Sensitivity analyses with cases counted starting immediately after the second dose of IP, 14 days after the first dose of IP, immediately after the first dose of IP, and immediately after randomization. • Vaccine efficacy and 95% CI based on the case incidence will be estimated with $1 - \text{ratio of incidence rates}$ using the exact method conditional upon the total number of cases.

 • Vaccine efficacy of mRNA-1273 to prevent COVID-19 in all study participants, regardless of evidence of prior SARS-CoV-2 infection 	
The FAS population will be used for this secondary objective, using similar analysis methods as for the primary endpoint analysis.
 
 • Primary analysis: VE will be estimated with $1 - \text{HR}$ (mRNA-1273 vs. placebo) using a Cox proportional hazard regression model with treatment group as a fixed effect and adjusting for stratification factor based on the FAS, with cases counted starting 14 days after the second dose of IP. • Sensitivity analyses with cases counted starting immediately after the second dose of IP, 14 days after the first dose of IP, immediately after the first dose of IP, and immediately after randomization.

Abbreviations: CI = confidence interval; COVID-19 = coronavirus disease 2019; FAS = Full Analysis Set; HR= hazard ratio; IP = investigational product; mITT = modified Intent-to-Treat; PP = Per Protocol; SARS-CoV-2 = severe acute respiratory syndrome coronavirus 2.

9.5.1.1. Efficacy Analysis on Primary Endpoint

To assess the primary efficacy endpoint of VE of mRNA-1273 in preventing the first occurrence of COVID-19 from 14 days after second dose of IP, Cox proportional hazards regression will be used to estimate proportional hazards VE (PH VE), measured by one minus the HR (mRNA-1273 vs. placebo), with a 2-sided score-based 95% CI and 2-sided p-value for testing $H_0: VE \leq 30\%$.

Vaccine efficacy is defined as the percent reduction in the hazard of the primary endpoint (mRNA-1273 vs. placebo). The VE will be estimated using one minus the HR (mRNA-1273 vs. placebo) estimand. A stratified Cox proportional hazard model will be used to assess the magnitude of the treatment group difference (ie, HR) between mRNA-1273 and placebo. The HR and its 95% CI from the stratified Cox model with Efron's method of tie handling and with treatment group as covariate will be reported. The same stratification factors used for randomization will be applied to the stratified Cox model.

For the primary efficacy endpoints, participants without documented COVID-19 will be censored at the last study assessment date. Potential intercurrent events may include: 1) death unrelated to COVID-19 and 2) early COVID-19 up to 14 days after second study dose.

In the estimand of the primary analysis on the primary endpoint, a hypothetical strategy will be used for death unrelated to COVID-19; a hypothetical strategy will also be used for early COVID-19, where the time to COVID-19 will be censored at the onset day of early case. The details of intercurrent event description and estimand strategies are presented in [Section 11.4.1](#).

For the primary efficacy analysis, cases will be counted starting 14 days after the second vaccination. Sensitivity analyses with cases counted immediately after the second vaccination, and after randomization will also be carried out.

Analyses of the primary endpoint will be also performed based on the mITT Set using the same methods described above.

For the primary efficacy analysis, cases will be counted starting 14 days after the second dose of IP. Sensitivity analyses with cases counted starting immediately after the second dose of IP and starting immediately after randomization will also be carried out.

Subgroup analysis of the primary efficacy endpoint will be performed in selected subgroups, such as age groups ≥ 18 and < 65 year and ≥ 65 years to assess consistency of VE as described in [Section 9.5.5](#).

As a supportive analysis, VE will also be estimated by one minus the infection rate ratio, where the number of cases (ie, participants with first occurrence of COVID-19) will be used and the CI will be computed using the exact method conditional upon the total number of cases. Cumulative incidence VE, one minus the ratio of cumulative incidences (mRNA-1273 vs. placebo) of

COVID-19, may also be assessed, the cumulative incidence for each arm will be estimated using a covariate adjustment method based on [Zeng \(2004\)](#) that makes use of baseline characteristics.

Additional analysis to evaluate VE against COVID-19 incorporating duration and presence/severity of symptoms will also be performed; the details will be provided in the SAP.

9.5.1.2. Efficacy Analysis on Secondary Endpoint

For each of the below secondary objectives:

- Vaccine efficacy to prevent severe COVID-19
- Vaccine efficacy to prevent serologically confirmed SARS-CoV-2 infection or COVID-19 regardless of symptomatology or severity
- Vaccine efficacy to prevent COVID-19 using a broad definition of symptoms
- Vaccine efficacy to prevent death caused by COVID-19
- Vaccine efficacy to prevent asymptomatic SARS-CoV-2 infection

For each of the above secondary objectives, the same Cox proportional hazard model described above for the primary objective will be applied using the PP Set, with cases counted starting 14 days after the second dose of IP. Sensitivity analyses with cases counted starting after the second dose of IP, 14 days after the first dose of IP, after the first dose of IP, and after randomization will also be performed.

The same model will be applied using the mITT population with cases counted starting 14 days after the second dose of IP.

Vaccine efficacy will be estimated with 1- ratio of incidence rates with the 95% CI using the exact method conditional upon the total number of cases.

Vaccine efficacy to prevent COVID-19 after the first dose of IP

The same Cox proportional hazard model described above for the primary objective will be applied using the PP Set, with cases counted starting 14 days after the first dose of IP.

Vaccine efficacy to prevent COVID-19 regardless of prior SARS-CoV-2 infection

The FAS will be used for analysis to evaluate VE to prevent COVID-19 regardless of prior SARS-CoV-2 infection. The same methods described above for the primary objective will be applied with cases counted starting 14 days after the second dose of IP. Sensitivity analyses with cases counted starting after the second dose of IP, 14 days after the first dose of IP, the first dose of IP, and randomization will also be performed.

Vaccine efficacy will be estimated with $1 - \text{ratio of incidence rates}$ with the 95% CI using the exact method conditional upon the total number of cases.

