To evaluate the efficacy of mRNA-1273 to prevent COVID-19 after the first dose of IP.	Vaccine efficacy of mRNA-1273 to prevent the first occurrence of COVID-19 starting 14 days after the first dose of IP.
To evaluate the efficacy of mRNA-1273 to prevent COVID-19 in all study participants, regardless of evidence of prior SARS-CoV-2 infection.	Vaccine efficacy of mRNA-1273 to prevent the first occurrence of COVID-19 starting 14 days after the second dose of IP regardless of evidence of prior SARS-CoV-2 infection determined by serologic titer against SARS-CoV-2 nucleocapsid (FAS analysis population, see Section 9.4).
To evaluate the efficacy of mRNA-1273 to prevent asymptomatic SARS-CoV-2 infection.	Vaccine efficacy to prevent the first occurrence of SARS-CoV-2 infection in the absence of symptoms defining COVID-19 starting 14 days after the second IP dose. SARS-CoV-2 infection determined by seroconversion assessed by bAb levels against SARS-CoV-2 as measured by a ligand-binding assay specific to the SARS-CoV-2 nucleocapsid protein and with a negative NP swab sample for SARS-CoV-2 at Day 1 (Section 8.1.1).

Objectives and Endpoints	
Immunogenicity Objective (Secondary):	Immunogenicity Endpoints (Secondary):
To evaluate the immunogenicity of 2 doses of mRNA-1273 given 28 days apart.	
 • GMT of SARS-CoV-2-specific nAb on Day 1, Day 29, Day 57, Day 209, Day 394, and Day 759. • GMFR of SARS-CoV-2-specific nAb relative to Day 1 on Day 29, Day 57, Day 209, Day 394, and Day 759. • Quantified levels or GMT of S protein-specific bAb on Day 1, Day 29, Day 57, Day 209, Day 394, and Day 759. • GMFR of S protein-specific bAb relative to Day 1 on Day 29, Day 57, Day 209, Day 394, and Day 759.
Immunogenicity Objective (Secondary) for Part C:	Immunogenicity Endpoints (Secondary) for Part C:

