The following events in a participant constitute absolute contraindications to any further dosing of the IP to that participant. If any of these events occur during the study, the participant must not receive additional doses of vaccine but will be encouraged to continue study participation for safety through end-of-study period as defined in [Section 4.4](#).

- Part A only: Diagnosed COVID-19 by detection of SARS-CoV-2 in a Day 1 NP swab sample or COVID-19 diagnosed prior to Day 29. If COVID-19 is suspected on or prior to Day 29, further administration of IP must be withheld until COVID-19 test results are available.
- Anaphylaxis or systemic hypersensitivity reaction following the administration of vaccine.
- Any SAE judged by investigator or Sponsor to be related to study vaccine.
- Any clinically significant medical condition that, in the opinion of the investigator, poses an additional risk to the participant if he/she continues to participate in the study.

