5.4. Per-Protocol Set

The Per-protocol Set consists of all participants in mITT who received planned doses of IP per schedule and have no major protocol deviations, as determined and documented by Sponsor prior to database lock (DBL) and unblinding, which impact critical or key study data. Participants will be analyzed according to the treatment group to which they were randomized. Participants who did not receive the second injection of IP within [21, 42] days after the first injection date will be excluded from the Per-Protocol Set.

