6.3.1.3. Sensitivity Analyses with COVID-19 Cases Counted Starting at Various Timepoints

Sensitivity analyses will be performed with COVID-19 cases counted starting at various timepoints as below using the PP Set. The censoring rules for analyses of the primary endpoint are summarized in Table 2.

- immediately after the second injection of IP
- 14 days after the first injection of IP (also as primary analysis approach for the secondary efficacy objective: To evaluate the efficacy of mRNA-1273 to prevent COVID-19 after the first dose of IP.)
- immediately after the first injection of IP
- immediately after randomization

If <10% of the COVID-19 cases received the first injection after the day the subject was randomized, sensitivity analysis with COVID-19 cases counted starting after the first injection of IP may not be performed separately, as it would be very similar to the sensitivity analysis with COVID-19 cases counted starting from randomization.

Table 2: Censoring Rules for COVID-19

Situation	Primary Efficacy Approach (cases ≥ 14 days after Dose 2)	Sensitivity Analyses			
		Cases starting after Dose 2	Cases ≥ 14 days after Dose 1	Cases starting after Dose 1*	Cases starting after randomization
Early case from randomization up to first injection	Censored at date of case	Censored at date of case	Censored at date of case	Censored at date of case	Event
Early case from Dose 1 up to ($<$) 14 days after Dose 1	Censored at date of case	Censored at date of case	Censored at date of case	Event	Event
Early case from ≥ 14 days after Dose 1 up to ($<$) Dose 2	Censored at date of case	Censored at date of case	Event	Event	Event
Early case from Dose 2 up to ($<$) 14 days after Dose 2	Censored at date of case	Event	Event	Event	Event
Case ≥ 14 days after Dose 2	Event	Event	Event	Event	Event
Early discontinuation or death without documentation of COVID-19	Censored at date of discontinuation/death				

Situation	Primary Efficacy Approach (cases \geq14 days after Dose 2)	Sensitivity Analyses			
		Cases starting after Dose 2	Cases \geq14 days after Dose 1	Cases starting after Dose 1*	Cases starting after randomization
Early infection as detected by: positive RT-PCR at scheduled visit (pre-dose 2), or, positive bAb against SARS-CoV-2 NP in blood samples at the scheduled visits	Censored at date of early infection				

* To be performed if there are \geq 10% of total cases with Dose 1 date > randomization date

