5.3.1.2.1. Effectiveness of the primary series

Effectiveness of the primary series of mRNA-1273 in those vaccinated participants, will be assessed in participants initially randomized to the mRNA-1273 group (mRNA-1273, vaccinated from July-December 2020, early vaccinated) and those initially randomized to the placebo group (Placebo-mRNA-1273, vaccinated December 2020-April 2021, recent vaccinated) using the PP Primary Series Set. Part A and Part B data after Dose 1 of mRNA-1273 will be included for this analysis, and date of Dose 1 of mRNA-1273 will be used as the reference. The analysis period will be from Dose 1 of mRNA-1273 to earlier of last study participation, booster date, or data cutoff date for efficacy as presented in Table 1.

Using PP Primary Series Set, participants at risk will be those who did not have evidence of prior infection prior to Dose 1 of mRNA-1273, specifically, those in mRNA-1273 (randomized to mRNA-1273 in Part A (baseline/pre-Day 1 SARS-CoV-2 negative is required for inclusion in PP Primary Series Set), and those in Placebo-mRNA-1273 group who were SARS-CoV-2 negative at PDV/unblinding at the start of Part B.

Incidence rates will be provided over the time from Dose 1 of mRNA-1273 to receipt of booster, last study participation, or data cutoff date for efficacy. Incidence rates will also be provided by calendar quarters, as well as by the following time intervals:

- After Dose 1
 - After Dose 1 of mRNA-1273
 - After Dose 1 to before Dose 2 of mRNA-1273
 - After Dose 2 of mRNA-1273
 - Dose 2 to <14 days after Dose 2
 - ≥ 14 days after Dose 2

The last time interval “ ≥ 14 days after Dose 2” of mRNA-1273 may be further partitioned into shorter intervals. For each interval, person-time is calculated for participants at risk at

the beginning of the interval, as the time from the date of the beginning of the time interval to the date of the event/censoring for subjects with an event/censor if the event/censor occurs in the interval; or the time of the interval for subjects who continue to be at risk at the end of the interval. Incidence rate, and 95% CI for incidence rate will be calculated using the exact method adjusting for person-time will be provided by treatment cohort. Number and incidence rates of COVID-19 starting 14 days after Dose 2 of mRNA-1273 will also be provided by calendar quarters.

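### The designated per-protocol analysis of efficacy after the first dose loses nearly all cases between the doses, so it approximates efficacy counted from Dose 2

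*Protocol*

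**What the plan says.** - **Endpoint.** Protocol section 3, Table 1: "Vaccine efficacy of mRNA-1273 to prevent the first occurrence of COVID-19 starting 14 days after the first dose of IP". No upper time limit is set, so cases after Dose 2 count too.
- **Designated analysis.** Protocol 9.5.1.2 has the Cox model "applied using the PP Set, with cases counted starting 14 days after the first dose of IP". Part A SAP 6.3.1.3 opens with "Sensitivity analyses will be performed with COVID-19 cases counted starting at various timepoints as below using the PP Set" and lists "14 days after the first injection of IP (also as primary analysis approach for the secondary efficacy objective". SAP 6.3.2.2 points back to that run.
- **Dosing rule.** Protocol 7.2 lists events that "constitute absolute contraindications to any further dosing of the IP to that participant". The first, marked as applying to Part A only, is "Diagnosed COVID-19 by detection of SARS-CoV-2 in a Day 1 NP swab sample or COVID-19 diagnosed prior to Day 29". If COVID-19 is suspected by Day 29, dosing waits for the result.
- **Analysis set.** Protocol 9.4 (Table 8) requires the planned doses per schedule. SAP 5.4 adds: "Participants who did not receive the second injection of IP within [21, 42] days after the first injection date will be excluded". SAP 6.3.1.2 repeats that missed doses lead to exclusion. None of these makes an exception for a dose withheld because of COVID-19.
- **Case coding.** SAP Table 2 codes a case from 14 days after Dose 1 up to Dose 2 as an event in this analysis.
- **mITT.** The text after SAP Table 2 repeats every start point in the mITT Set. Protocol Table 9 also lists an mITT analysis, but its generic text counts this endpoint from 14 days after the second dose, against Table 1 and 9.5.1.2.
- **Part B/C SAP.** Section 5.3.1.2.1 tabulates incidence for the interval "After Dose 1 to before Dose 2 of mRNA-1273" in the PP Primary Series Set, which (section 4.6) requires two doses on schedule.

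**The concern.** The dosing rule and the set definition act together. A Part A participant diagnosed with COVID-19 between the doses is refused Dose 2, and without Dose 2 is not in the PP Set. Participants are thus removed because they had the outcome being counted, and the Table 2 row that codes them as events is nearly empty. The stretch from 14 days after Dose 1 to Dose 2 becomes almost event-free in both arms, and it is the only part of follow-up that separates this objective from an analysis counted from Dose 2. At stake is the VE estimate reported for a stated secondary objective. The PP runs counted from Dose 1 or from randomization share the defect.

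**Working it through.** **1. The plan's own figure.** The documents state no figure for VE after the first dose, so I first reproduced the design behind the case counts. Inputs (protocol 9.3): VE 60% against a null of 30%, 1-sided 0.025, 90% power, 1:1 allocation, looks at 35% and 70%, placebo incidence 0.75% per 6 months, 2% annual dropout, 15% excluded from PP, 3-month uniform accrual.

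The vaccine share of cases is p0 = 0.7/1.7 = 0.412 under the null and p1 = 0.4/1.4 = 0.286 under the alternative.

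Events = [1.960/√(p0(1−p0)) + 1.282/√(p1(1−p1))]² / [ln(0.4/0.7)]² = (3.982 + 2.837)²/0.3132 = 148.5. Multiplying by 1.014 for the O'Brien-Fleming spending gives 150.6, which matches the planned 151. The same inputs put 53, 106 and 151 cases at 5.3, 7.6 and 9.7 months, against the stated 5, 8 and 10.

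**2. Which between-dose cases can stay in PP.** Only those not diagnosed before Dose 2. A symptomatic case found only on the Day 29 pre-dose swab is one. Its date is the later of the PCR and symptom dates (SAP 6.3.1.1), so with Dose 2 on the same day it falls on or after Dose 2 and outside the between-dose row. A participant dosed in deviation from the rule could also stay.

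**3. Size under design inputs.** Per arm 25,500/2 = 12,750, used for both sets so that the contrast isolates the lost cases. Monthly placebo hazard = −ln(1−0.0075)/6 = 0.001255; 14 days = 0.460 months. Between-dose placebo cases b = 12,750 × 0.001255 × 0.460 = 7.4. Expected cases from 14 days after Dose 2 (P placebo, V vaccine) are 112.7 and 45.2 at 10 months, and 33.8 and 13.5 at 5 months.

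Let VE1 be VE between the doses and VEm be VE in the 14 days after Dose 2, whose cases stay in both sets. Both are assumptions.

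- mITT: VE = 1 − [V + b(1−VE1) + b(1−VEm)]/(P + 2b)
- PP: VE = 1 − [V + b(1−VEm)]/(P + b)

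Example (10 months, VE1 0%, VEm 60%): mITT 1 − (45.2+7.4+2.9)/127.4 = 56.4%; PP 1 − (45.2+2.9)/120.1 = 59.9%.

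| VE1 | VEm | 10 mo: mITT / PP | 5 mo: mITT / PP |
|---|---|---|---|
| 0% | 0% | 53.0 / 56.2 | 41.8 / 49.2 |
| 0% | 60% | 56.4 / 59.9 | 50.9 / 60.0 |
| 30% | 30% | 56.4 / 58.1 | 50.9 / 54.6 |
| 30% | 60% | 58.2 / 59.9 | 55.4 / 60.0 |
| 60% | 60% | 59.9 / 59.9 | 60.0 / 60.0 |

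**4. Size with high efficacy and short follow-up.** The Part B/C SAP (2.1) gives VE 94.5% at the 95-case interim analysis, and Part A SAP 6.4.2.1 gives median follow-up of 49 days. I assume those days run from Dose 2, leaving 49 − 14 = 35 days in the primary risk period. With a constant placebo hazard, cases are proportional to days:

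- mITT: VE = 1 − [14(1−VE1) + 14(1−VEm) + 35×0.055]/63
- PP: VE = 1 − [14(1−VEm) + 35×0.055]/49

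| VE1 | VEm | mITT | PP | Gap (points) |
|---|---|---|---|---|
| 50% | 50% | 74.7 | 81.8 | 7.1 |
| 50% | 94.5% | 84.6 | 94.5 | 9.9 |
| 80% | 80% | 88.1 | 90.4 | 2.3 |
| 80% | 94.5% | 91.3 | 94.5 | 3.2 |
| 94.5% | 94.5% | 94.5 | 94.5 | 0 |

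**5. Simulation.** Forty simulated trials at three times the design incidence, VE 30% until 14 days after Dose 2 and 60% thereafter, with every between-dose case removed from PP. Mean VE was 56.2% (mITT from 14 days after Dose 1), 57.8% (PP, same start), 57.8% (PP from Dose 2) and 59.5% (PP from 14 days after Dose 2). The two middle analyses agreed exactly in every trial, as they must, because an interval without events adds nothing to the Cox partial likelihood.

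**6. Part B/C interval.** The contraindication applies to Part A only. In Part B, protocol 7.1 treats COVID-19 as a criterion for delay, and the OL-D29 window is −3/+14 days. A crossover participant with COVID-19 between doses can therefore receive Dose 2 within 21 to 42 days and stay in the PP Primary Series Set. The Part A cohort loses nearly all such cases; the crossover cohort loses only those whose Dose 2 is missed or out of window.

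**The case against.** The strongest reply is that the missing cases are already analysed. The mITT repeat covers every start point, and FAS analyses from 14 days after the first injection and from randomization are planned as well (SAP 6.3.2.2). That stands, and it reduces the Part A defect to which prespecified analysis answers the objective. It does not remove it, because protocol 9.5.1.2 names only the PP Set for this objective and the SAP calls that run the primary approach.

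It is also fair to say that Part A is finished, with a clinical study report dated 3 August 2021, so changing the main population now is a choice made after unblinding. The fix has to say so. The endpoint is outside the fixed sequence in SAP 6.5, so an estimate is affected and no error rate is.

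Four stronger readings are tempting and not supported:

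- A reader might infer that the endpoint was meant as one-dose VE. Table 1 sets no upper limit, so even the mITT analysis mixes one-dose and two-dose follow-up.
- A reader might infer that the PP result simply equals the two-dose 94.5%. Cases from Dose 2 to 14 days later remain in PP and can lower it, as the tables show.
- A reader might combine 94.5% with the 196 cases of the primary analysis. The documents attach 94.5% to 95 cases and give no VE for the 196.
- A reader might carry the same loss over to the crossover cohort in Part B. The dosing rule there is different.

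**Conclusion.** Wrong as written. The designated PP analysis of efficacy after the first dose selects on its own outcome and comes close to an analysis counted from Dose 2. The direction is upward if between-dose protection is lower than protection after Dose 2, and null if they are equal. The documents do not give between-dose VE, so every size rests on assumption: about 0 to 4 points at 10 months and up to about 9 at 5 months under design inputs (VE1 from 0 to 60%); about 7 to 10 points (VE1 50%) or 2 to 3 points (VE1 80%) with 94.5% after Dose 2 and 35 days at risk. The primary endpoint, its conclusion and type I error are not touched. In the Part B/C SAP the between-dose interval is not comparable across the two cohorts, because they lose cases under different rules.

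**What to change.** - **Part A.** Report the prespecified mITT analysis as the main result for this objective and for every analysis that counts cases before Dose 2. Label the PP versions as conditional on receiving Dose 2. State openly that, with Part A complete, this changes which prespecified result is reported for the objective.
- **One-dose VE.** If that quantity is wanted, add an interval estimate from 14 days after Dose 1 to Dose 2.
- **Part B/C SAP 5.3.1.2.1.** For the interval before Dose 2, use a set requiring Dose 1 of mRNA-1273 and negative pre-Dose 1 status, but not Dose 2.
- **Reconcile** protocol 7.2, 9.4 (Table 8), Table 9 and 9.5.1.2 with SAP 5.4 and 6.3.1.3 (Table 2), including the second-dose start point in Table 9. No dosing rule needs to change.

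Cost: wording for Part A, since the mITT runs are already planned; one added analysis set and rerun interval tables for Part B/C. The reported VE after the first dose may be less favourable.
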